2 INTRODUCTION

2.1 BACKGROUND & STUDY RATIONALE

Chronic post-traumatic headache (CPTH) after a mild traumatic brain injury (mTBI) is extremely debilitating, dramatically impacts function and quality of life, and is the most frequent type of chronic pain reported after injury.¹ It has been estimated that approximately 17.1 million Americans suffer a traumatic brain injury (TBI) each year,² with CPTH estimated to occur in 57.8% of these individuals.³ CPTH presents as: 1) tension-like (mild-moderate dull pain), 2) migraine headache (moderate-severe throbbing pain), or 3) combined tension-like and migraine headache.¹ On average, the number of reported headache days each month for individuals suffering from CPTH is 26,⁴ which is almost daily. Individuals suffering from CPTH are more likely to have post-traumatic stress disorder, cognitive symptoms, and somatic symptoms.⁴ They are also more likely to perceive difficulties in their physical and social function.⁴ Consequently, it is not surprising that CPTH is extremely agonizing and frustrating for individuals with mTBI.

There are currently no FDA approved pharmacological treatments specifically for CPTH and the long-term effects of pharmacologic treatments on recovery after TBI are unclear. Thus, individuals are typically prescribed medications that target the particular type of headache (e.g. triptan for a migraine headache). Non-narcotic analgesics, nonsteroidal anti-inflammatory drugs (NSAIDs), and triptans are often prescribed for headache and migraine treatment and have been recommended to be coupled with non-pharmacological treatments, such as physical therapy, biofeedback, and relaxation training. However, because the long-term effects of pharmacologic treatments on recovery after TBI are unclear, non-pharmacologic or behavioral treatments for CPTH are very appealing.

As an alternative, acupuncture is a non-pharmacologic treatment that has been explored for CPTH. Acupuncture has been practiced in Chinese medicine for over 4,000 years. It is a technique where fine needles are inserted into specific areas of the body to achieve a therapeutic benefit. Historically, acupuncture is based on a Chinese/East Asian medical theory that acupuncture restores normal function to the body by balancing Qi. Although the mechanism of acupuncture is not fully understood, previous research has shown that it has a regulating effect on the nervous system and it has been effective for treating a wide range of chronic pain conditions, including headaches and migraines.

Acupuncture has been shown to be safe and effective treatment for individuals suffering from headaches and migraines. Acupuncture has been used and reported by physicians in the United States as early as the 1600s and has been researched since the 1800s. Most of the early reports were of individual patient cases, whereas the first randomized controlled trial of acupuncture treatment was published in 1975. While there are still many theories regarding the mechanism of acupuncture, research has provided evidence for the benefits of acupuncture in several medical indications, including for migraine and tension headache. Acupuncture has been shown to be efficacious for both acute migraine treatment, migraine prophylaxis, and tension headache treatment. In addition, acupuncture has been shown to be more effective than, or as effective as pharmacotherapy with fewer side effects. It has also been shown to decrease migraine and tension headache. Importantly, reduce pain intensity, that also been shown to decrease migraine and tension headache. Importantly, the safety of acupuncture has been well documented. Although both minor and serious adverse events (AEs) have been reported, serious complications related to acupuncture are rare.

While acupuncture is currently well-accepted as a behavioral treatment for individuals with chronic pain, headaches, and migraines, ⁹ it has not been extensively examined in individuals with CPTH. Although there have been studies as early as the 1980s that have shown improvements in headache symptoms with acupuncture for individuals who have suffered from mTBI, ^{16,17} there have been a limited number of studies since. In two recent case reports, acupuncture combined improved acute post-traumatic headache symptoms in an individual who suffered a mTBI. ^{18,19} In another recent study, acupuncture improved headache-related quality of life and reduced overall pain in adult service members with mild-to-moderate TBI suffering from CPTH. ²⁰ Therefore, although there is a paucity of research examining acupuncture for CPTH, it has shown efficacy in patients with chronic headaches and migraines, ¹¹ and researchers have suggested that it be investigated and considered for treatment of CPTH. ²¹ In addition, while they did not examine CPTH specifically, four randomized controlled trials investigated acupuncture treatment in individuals with TBI and reported no AEs. ²² Thus, acupuncture could potentially be a safe and viable alternative to medication for individuals with mTBI suffering from CPTH.

Because acupuncture for CPTH has not been extensively examined, there is also no consensus on the number of acupuncture sessions that are necessary for improvement. In the study of service members with mild-to-moderate TBI suffering from CPTH, 10 sessions of acupuncture were administered over 6 weeks. ²⁰ Because the two case studies were examining acupuncture for acute post-traumatic headache, ^{18,19} the specific treatment methods may not be applicable for CPTH. In a recent review of acupuncture for chronic headaches and migraines, 6-10 weekly or twice-weekly acupuncture sessions were reported to be most effective. ²¹ However, the amount of acupuncture necessary for improvement in individuals suffering from CPTH is unclear. Thus, the primary goal of this study is to determine the effect of a low versus high dose of acupuncture treatment on number of headache days for individuals suffering from CPTH.

2.2 RISK/BENEFIT ASSESSMENT

2.2.1 KNOWN POTENTIAL RISKS

Acupuncture Treatment

Reported Side Effects²³:

Common 1-10 out of 100 people	Uncommon 1-10 out of 1,000 people	Rare 1-10 out of 10,000 people	Very Rare <1 out of 10,000 people
Bleeding	Inflammation/swelling	Local infection	Palpitations
Hematoma (bleeding outside of vessels)	Bruising	Redness	Constipation
	Pain during needling	Itching	Diarrhea
	Local muscle pain	Sweating	Gastrospasm (stomach spasm)
	Nerve irritation or injury	Decrease/increase of blood pressure	Enterospasm (spasm of the intestine)
	Headache	Unconsciousness	Weight loss
	Fatigue	Tachycardia	Circulatory disturbance
	Dizziness	Breathing difficulties	Lesion of blood vessels
	Nausea	Vomiting	Systemic infection

Exacerbation of symptoms that led to treatment	Worsening health state	Euphoria
	Generalized muscle pain	Nightmares
	Restricted movement	Poor concentration
	Joint problems	Imbalance
	Feeling of coldness	Disturbance of speech
	Menstrual problems	Disorientation
	Depressive mood	Shivering
	Anxiety	Eye irritation
	Sleep disturbance	Broken (retained) needles
	Restlessness/nervousness	Organ puncture/ Pneumothorax
	Disturbed vision	Injury of the central nervous system
	Tinnitus	Injury of the pericardium

Additional potential risks specific to electroacupunture treatment and minimization of these risks Potential risks²⁴:

- Increased depth and altered angulation of needles to ensure needles can support the weight of the leads and clips.
 - We plan to use microclips, which are much lighter than alligator clips, so this risk will be dramatically minimized.
- Vigorous muscle contraction causing needle movement (e.g. need drawn deeper into the body).
 - The goal of acupuncture treatment in this study is not to illicit a muscle twitch. The goal is to induce a mild level of sensation, which typically does not cause muscle contraction. Thus, we do not anticipate vigorous muscle contractions or unsafe needle movement.
- Minor risks have been reported for acupuncture treatment of the abdominal muscles, over the rib cage, the carotid sinus, the laryngeal muscles, and the vagus nerve.
 - o For this study, we will not be performing acupuncture treatment in any of these areas, so we do not anticipate these risks.
- Risk of cardiac arrest with excessive current (risks reported around 50mA).
 - The Pantheon Research 8c. Pro stimulator we will use for this study has a current range of 0-15 mA, therefore we will be simulating with a current that is much lower than the range for this risk.
 - There is also a risk of excessive current if electrostimulation devices are plugged into the main electrical supply. The Pantheon Research 8c.Pro stimulator that we will use for this study is battery operated, therefore we do not anticipate this risk.
- Interference with implantable cardioverter defibrillators, pacemakers, or other implantable devices.
 - We have minimized this risk for our study by excluding anyone with a history of cardiac arrhythmia or current pacemaker, neurostimulator, or other implanted stimulation device.
- Seizures
 - We have minimized this risk for our study by excluding anyone with a history of seizures.

o In addition, there have not been any reports linking electroacupuncture to seizures.

Assessments/Questionnaires (Headache Diary, PSQI, & TBI-QOL)

Participants will be asked to complete a headache diary 3 times, each time for a duration of 4-weeks. This may be difficult or tiring for participants. The PSQI and the Traumatic Brain Injury-Quality of Life (TBI-QOL) are standardized questionnaires that will measure personal perception of life and sleep quality. The questions on these assessments may make participants feel uncomfortable because some parts may be easy to answer, while some parts may be difficult or tiring. Filling out the questionnaires may also cause individuals to feel uncomfortable or upset.

Loss of Confidentiality

There may be a slight possibility of breach of confidential information that was collected. However, the following procedures will be implemented to reduce this risk:

- Data collection and reporting tools will be developed and stored internally.
- Data collected and stored electronically will remain confidential and secure (e.g. secured server and password protected files [REDCap]).
- Study binders will be stored in a locked file cabinet within a locked office.
- After the study is closed, all subject identifiers will be destroyed.

2.2.2 KNOWN POTENTIAL BENEFITS

Acupuncture has been shown to be a safe and effective treatment for individuals suffering from headache and migraines. Although there is less evidence for individuals with mTBI suffering from CPTH, acupuncture treatment may provide headache relief to patients.

2.2.3 ASSESSMENT OF POTENTIAL RISKS AND BENEFITS

We believe the potential risks to the participants in this study are minimal and that the benefit of understanding how much acupuncture treatment is needed for headache relief in individuals with CPTH outweighs the potential risks.

3 OBJECTIVES AND ENDPOINTS

OBJECTIVES	ENDPOINTS
Primary	
To determine the effect of a low versus high dose of acupuncture on number of headache days per month in individuals with mTBI suffering from CPTH.	Number of headache days over 4 weeks
Secondary	
To determine the safety and tolerability of acupuncture on CPTH in individuals with mTBI.	Adverse or Serious Adverse Events Completion of treatment durations and sessions
Exploratory	
To explore the effects of acupuncture on sleep, quality of life, headache outcomes, and	 Pittsburgh Sleep Quality Index Traumatic Brain Injury-Quality of Life

OBJECTIVES	ENDPOINTS
medications in individuals with mTBI who suffer	3. Headache Outcomes
from CPTH.	4. Medications

4 STUDY DESIGN

4.1 OVERALL DESIGN

Study Design:

This study is an unblinded, uncontrolled randomized, 2-arm clinical trial.

Hypotheses:

Primary Hypothesis: We hypothesize that both treatment groups will have decreased headaches. **Secondary Hypothesis:** We hypothesize that acupuncture will be safe and tolerated in both groups.

Randomization:

Prior to the first acupuncture treatment visit, participants will be randomized into two treatment groups. Randomization is explained in **Section 6.3**.

Acupuncture Treatment Groups:

Group 1: 18 participants will receive acupuncture treatment 1x per week for 5 weeks = 5 total. **Group 2:** 18 participants will receive acupuncture treatment 2x per week for 5 weeks = 10 total.

Study Intervention:

Acupuncture treatment will consist of a standardized treatment protocol designed for this study. Specifically, 18 needles will be inserted into specific areas of the body for a duration of 30 minutes. Additional details of the treatment are discussed in **Section 6.1**.

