1.2 SCHEMA

Pre-screen potential participants by inclusion and Pre-screening exclusion criteria. Phone Call Schedule Pre-treatment Visit. **Pre-treatment Visit** Conduct informed consent process. Perform baseline assessments: Visit 1 Pittsburgh Sleep Quality Index (PSQI) (Day 1) Traumatic Brain Injury-Quality of Life (TBI-QOL) short forms Medication Review Randomize N = 36Arm 1 Arm 2 N = 18N = 18Study intervention (Low Dose) Study intervention (High Dose) Acupuncture treatment Acupuncture treatment Visits 2-6 [Arm 1] 1x/week for 5 weeks (5 total) 2x/week for 5 weeks (10 total) Visits 2-11 [Arm 2] Completed Headache Diary Completed Headache Diary (Days 29 + 14 to Adverse Events Reporting Adverse Events Reporting 64 + 14)**Medication Review Medication Review** Treatment Adherence Treatment Adherence 4-week Post-treatment Visit Perform assessments: Completed Headache Diary Visit 7 [Arm 1] Adverse Events Reporting Visit 12 [Arm 2] (Day 71-106 + 7) Medication Review **PSOI** TBI-QOL short forms 12-week Post-treatment Visit Perform final assessments: Completed Headache Diary Visit 8 [Arm 1] Adverse Events Reporting Visit 13 [Arm 2] Medication Review (Day 127-169 + 7) TBI-QOL short forms

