 - © E-mail the Pittsburgh Sleep Quality Index (PSQI) and Traumatic Brain Injury-Quality of Life (TBI-QOL) surveys to the patient for completion. Ask patients to complete the surveys prior to their first acupuncture visit. During the reminder call for the acupuncture visit, patients will be reminded to complete the surveys if they have not yet completed them.
 - Provide participants instructions regarding the Headache Diary REDCap survey (example script below):
 - "You will receive a Headache Diary survey via e-mail once a week for the next 4 weeks. Each survey will ask questions about your headaches over the last week. What is most important for you to remember is the number of headaches you had. The rest of the information is also helpful."
 - 2. Provide participants a paper diary and ask them to use it to keep track of their headaches during the week. Instruct participants that they should use it to fill out the weekly e-mail survey.
 - 3. Show participants an example of the REDCap survey.

3. Study Intervention

- Duration: Each visit approximately 1 hour
- A study acupuncturist will:
 - Complete the Adverse Events (AE) Reporting, Medication Review, and Treatment Adherence in the relevant eCRFs in REDCap.
 - o Perform the acupuncture treatment.
- Only at the LAST acupuncture visit, a study acupuncturist will:
 - Provide participants instructions regarding the Headache Diary REDCap survey (example script below):
 - "Like you experienced before, you will receive a Headache Diary survey via e-mail once a week for the next 4 weeks. Each survey will ask questions about your headaches over the last week. What is most important for you to remember is the number of headaches you had. The rest of the information is also helpful."

2. Provide participants a paper diary and ask them to use it to keep track of their headaches during the week. Instruct participants that they should use it to fill out the weekly e-mail survey.

3. Show participants an example of the REDCap survey.

4. 4-week Post-treatment Visit

- Duration: Approximately 30 minutes via phone
- Research staff will:
 - Complete the AE Reporting and Medication Review forms in the relevant eCRFs in REDCap.
 - o E-mail the PSQI and TBI-QOL surveys to the patient for completion. Ask patients to complete the surveys within one week. Five days after the visit, patients will receive a reminder call if they have not yet completed the surveys.

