5.4 SCREEN FAILURES

Pre-screening Phone Call:

All potential participants will undergo a pre-screening phone call to determine whether they meet the inclusion/exclusion criteria. Patients will be considered ineligible if they do not meet one or more of the inclusion/exclusion criteria during pre-screening. We will collect information on why participants are ineligible or decide not to move forward with the trial.

Pre-treatment Visit:

Screen failures are defined as participants who are considered eligible during the pre-screening phone call, but it was subsequently determined that they do not meet one or more of the inclusion/exclusion criteria at or after the Pre-treatment (baseline) visit. We will collect information on why participants screen fail or decide not to move forward with the trial.

Rescreening Patients:

Individuals who do not meet the criteria for participation in this trial (ineligible or screen failure) because of meeting one or more exclusion criteria that are likely to change over time may be rescreened up to one time. Examples include: successful treatment for a substance use disorder; women who are no longer pregnant, lactating, or planning to become pregnant; or participation in an interventional study≥3 months prior. Rescreened participants will be assigned a new participant number.

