6.3 MEASURES TO MINIMIZE BIAS: RANDOMIZATION AND BLINDING

Randomization:

Randomization will be performed with a 1:1 allocation ratio. Balanced treatment assignments will be achieved using permuted block randomization with random block sizes stratified by gender. This decision was based on evidence that females in this population reported higher rates of headaches.³³ The study biostatistician will generate a randomization schedule using the SURVERYSELECT procedure in SAS. Assignments will not be seen by other study personnel in advance and will not be changed after randomization.

Blinding:

Study personnel will be unblinded to the randomization, as it will be clear the number of participants who receive 5 acupuncture treatments versus those that receive 10. In addition, it will be clear to participants which treatment group they are in and it will be impossible to blind them from this information.

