7.2 PARTICIPANT DISCONTINUATION/WITHDRAWAL FROM THE STUDY

Participants are free to withdraw from participation in the study at any time upon request. An investigator may discontinue a participant from the study for the following reasons:

- 1. Participant has not completed an acupuncture treatment for > 14 days, unless a participant has an illness, such as COVID-19. In this case, additional time may be allowed, as determined by the investigator.
- 2. Significant study intervention non-compliance
- 3. Lost-to-follow up; unable to contact subject (see Section 7.3, Lost to Follow-Up)
- 4. Any event or medical condition or situation occurs such that continued collection of follow-up study data would not be in the best interest of the participant or might require an additional treatment that would confound the interpretation of the study
- 5. The participant meets an exclusion criterion (either newly developed or not previously recognized) that precludes further study participation

The reason for participant discontinuation or withdrawal from the study will be recorded on the relevant eCRF. Subjects who sign the informed consent form and are randomized but do not receive the study intervention may be replaced. Subjects who sign the informed consent form, and are randomized and receive the study intervention, and subsequently withdraw, or are discontinued from the study, will not be replaced.

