8 STUDY ASSESSMENTS AND PROCEDURES

8.1 ENDPOINT AND OTHER NON-SAFETY ASSESSMENTS

Demographics: Demographic information will be collected, including: gender, age, race, ethnicity, language, height, weight, marital status, employment status, date of TBI, date of CPTH diagnosis, and email address for Headache Diary surveys (discussed below).

Medication Review: Medication data will be used for exploratory purposes for Specific Aim 3.

Headache Diary: Participants will be sent an e-mail REDCap survey to complete and asked to record headache information for three 4-week time periods. During each 4-week period, they will receive the e-mail once per week. They will be provided paper headache diaries (Appendix 1-3) to keep track of their headaches and will be asked to complete each e-mail survey they receive. The headache diary survey will include: how many headaches occurred each week during the 4-week period, duration, pain intensity (0-10 scale), type (e.g. tension), and name of medication taken and dosage (if applicable). The outcome measure for Specific Aim 1 is number of headache days over 4 weeks; other variables will be exploratory.

Treatment Adherence: The participant's treatment adherence will be measured to determine tolerability of acupuncture. We will record the number of attended acupuncture sessions. We will also record participants' ability to maintain the acupuncture duration of 30 minutes per session.

Sleep: Participants will be asked to complete the Pittsburgh Sleep Quality Index (PSQI), which contains questions about one's usual sleep habits during the past month.

Quality of Life: Participants will be asked to complete the TBI-QOL short forms. The TBI-QOL includes the following domains: ability to participate in social roles and activities, anger, anxiety, attention-concentration, cognition-general concerns, communication, depression, emotional behavior dyscontrol, executive function, fatigue, grief-loss, headache pain, independence, learning-memory, mobility, pain interference, positive affect and well-being, resilience, satisfaction with social roles and activities, self-esteem, stigma, and upper extremity.

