9.4.2 ANALYSIS OF THE PRIMARY ENDPOINT(S)

The number of headache days per 4 weeks will be captured via a headache diary. The primary outcome, change in number of headache days per 4 weeks between the pre-treatment assessment and 4-week post treatment assessment, will be compared using a two sample t-test. We will present the mean change by group with corresponding standard deviations. If baseline differences are found between study groups, they will be adjusted for using a linear regression model. In addition, a mixed-model analysis of variance (ANOVA) will be performed with data from all three time points. The outcome will be number of headache days per 4 weeks and it will be adjusted for group, time, and a group*time interaction. If significant interactions exist, line plots and post hoc tests will be used to define the nature of the interaction.

Prior to analysis, we will plot our outcomes to examine their distribution and decide whether we should consider non-parametric analyses. Only subjects with complete data from both pre-treatment assessment and 4-week post treatment assessment will be included in the final analysis. Data will be analyzed per an intent-to-treat approach regardless of actual treatment received. If a large proportion of missing data is noted, we will compare baseline characteristics of subjects who completed the treatment with those who were lost to follow-up.

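### As scheduled, randomisation precedes the 4-week baseline headache diary and nothing withholds the arm, so the baseline of the primary change outcome can be reported with knowledge of allocation

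*Combined protocol and SAP*

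**What the plan says.** **When randomisation happens.** Section 4.1: "Prior to the first acupuncture treatment visit, participants will be randomized into two treatment groups". The grid in 1.3 ticks Randomization only under the Pre-treatment Visit (Visit 1). The Schema in 1.2 labels that visit Day 1 and runs straight on to the next step, "Medication Review Randomize N = 36Arm 1 Arm 2", with treatment visits from Day 29 + 14.

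**When the baseline is recorded.** At the Pre-treatment Visit participants are told "You will receive a Headache Diary survey via e-mail once a week for the next 4 weeks". Section 8.1 has them "asked to record headache information for three 4-week time periods"; the first of these is the baseline. The baseline PSQI and TBI-QOL are e-mailed at the same visit and may be returned at any time before the first acupuncture session.

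**Who knows the arm.** Section 6.3: "it will be clear to participants which treatment group they are in". Its one concealment rule stops other study personnel seeing assignments in advance. It does not say when participants are told.

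**What the primary analysis uses.** Section 9.4.2 takes the change in headache days from the pre-treatment diary to the 4-week post-treatment diary, and adds: "Only subjects with complete data from both pre-treatment assessment and 4-week post treatment assessment will be included in the final analysis".

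**What happens to early losses.** Section 7.2: "Subjects who sign the informed consent form and are randomized but do not receive the study intervention may be replaced". Section 5.4 also counts as a screen failure anyone for whom "it was subsequently determined that they do not meet one or more of the inclusion/exclusion criteria at or after the Pre-treatment (baseline) visit".

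**The concern.** A baseline is safe to subtract because it is measured before allocation can influence it. Here the whole first diary follows the scheduled point of randomisation, the diary is self-reported, and the two arms ask for visibly different commitments (5 or 10 visits). If knowing the arm changes what people record, the difference passes straight into the between-arm difference in change. The shift could go either way: it could create an apparent dose effect or hide a real one.

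The same ordering moves run-in losses to the wrong side of randomisation. Someone who never completes the baseline diary, or who leaves before the first session, has already been allocated. The first is then dropped by the complete-case rule in 9.4.2 and the second may be replaced under 7.2, although 9.3 and 9.4.2 both call the analysis intention-to-treat. If such losses depend on the arm, the comparison loses some of the protection of randomisation before any treatment is given.

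**Working it through.** **1. Timeline.** Visit 1 is Day 1 (1.2), and randomisation is ticked there (1.3). The diary covers the next 4 × 7 = 28 days. Treatment starts between Day 29 and Day 29 + 14 = Day 43. The scheduled gap from randomisation to treatment is therefore 29 − 1 = 28 to 43 − 1 = 42 days, and the full baseline diary lies inside it. Participants are aware of the arm during this time only if they have been told it, which the documents neither state nor prevent.

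**2. The plan's own power.** Inputs from 9.2: two-sided two-sample t-test, alpha 0.05, n = 18 per arm, SD 4.47 (4.5 in the tables), target difference 4.5 days. With λ = d / (SD × √(2/n)), power is the probability that a noncentral t on 34 df exceeds the critical value in absolute size.
- SD 4.47: λ = 4.5 / (4.47 × 0.3333) = 3.02, power 0.835, as stated.
- SD 4.5: λ = 4.5 / 1.5 = 3.00, power 0.830.

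**3. Effect of a differential baseline shift.** Let arm knowledge move mean reported baseline by b days in one arm relative to the other, with no true effect. A change score carries b one-for-one, so λ = b / 1.5 at an SD of change of 4.5. The documents give no value for b; the range below is an assumption.

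| b (days) | λ | False-positive rate |
|---|---|---|
| 0 | 0 | 5.0% |
| 0.5 | 0.33 | 6.2% |
| 1 | 0.67 | 9.9% |
| 1.5 | 1.00 | 16.3% |
| 2 | 1.33 | 25.4% |

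Using 4.47 instead gives 10.0%, 16.5% and 25.7% for 1, 1.5 and 2 days. With a true 4.5-day effect, a 1-day shift against it lowers power from 83.0% to 62.1%; a 1-day shift in its favour raises power to 94.5%.

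**4. Sensitivity to the SD.** Section 9.2 uses its SD for mean headache days, and 9.4.2 analyses change. If 4.5 is the SD at one time point and r is the baseline/follow-up correlation, the SD of change is 4.5 × √(2(1 − r)). For b = 1:
- r = 0.3: SD 5.32, false-positive rate 8.5%
- r = 0.5: SD 4.50, 9.9%
- r = 0.7: SD 3.49, 13.3%
- r = 0.8: SD 2.85, 17.6%

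**5. Does baseline adjustment cure it?** With equal SDs the regression slope is r, so the residual bias is r × b and the residual SD is 4.5 × √(1 − r²). For b = 1 (33 df, ignoring the slight loss of precision from the baseline imbalance):
- r = 0.5: bias 0.5, SD 3.90, λ = 0.5 / (3.90 × 0.3333) = 0.38, false-positive rate about 6.6%
- r = 0.8: bias 0.8, SD 2.70, λ = 0.8 / (2.70 × 0.3333) = 0.89, about 13.9%

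Adjustment helps, but less as the correlation rises. Section 9.4.2 applies it only if baseline differences are found, so an arm-induced difference could itself trigger it.

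**6. Losses.** From 40 randomised, at SD 4.5 and a 4.5-day effect, power is 0.869 with no loss, 0.830 with 36 left and 0.781 with 32 left. The loss of power is modest. The larger issue is whether the people lost differ by arm, which no calculation from the documents can settle.

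**The case against.** **The timing is not firmly Day 1.** Section 4.1 would allow randomisation at the end of the run-in. The Visit 1 task list mentions neither randomising nor telling the participant the arm. A Visit 1 tick does not prove same-day completion, since the PSQI and TBI-QOL are ticked there and may be returned later. Section 5.5 expects 50 to consent and 40 to be randomised, which could reflect a delay, although screen failure at Visit 1 explains it equally well. This stands in part: the documents are ambiguous. But the only two places that locate randomisation put it before the diary, and none says otherwise.

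**Arm knowledge during the diary is inferred.** This stands. A reader might conclude that every participant records the baseline knowing the arm, for 28 to 42 days. That assumes disclosure on the day of randomisation, which no section states, and the diary itself covers only 28 days.

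**The error rates depend on an invented shift.** This also stands. The plan expects about 26 headache days out of 28, so upward over-reporting has roughly 28 − 26 = 2 days of average headroom, and an upward shift of 2 days would need almost everyone at the ceiling. Downward shifts are not limited in this way.

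**The endpoint may not be change.** Sections 3 and 9.2 describe headache days over 4 weeks, and a comparison of follow-up alone would not be affected by a baseline shift. But 9.4.2 explicitly names change as the primary outcome.

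**Replacement, screen failure and complete cases are separate matters.** Largely true: they exist whenever randomisation occurs, rescreening is allowed once and only for exclusion criteria likely to change, and 7.2 does not say that replaced people leave the analysis. They belong here only because the present order makes run-in losses post-randomisation losses.

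**Unblinding is already acknowledged as a limitation (4.2).** Unblinded treatment is unavoidable in this design; an unblinded baseline is not.

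**Conclusion.** The concern holds in this form: followed as scheduled, the plan permits an arm-aware baseline for the primary change outcome and for the baseline PSQI and TBI-QOL, and it places pre-treatment losses after randomisation. The size and direction of any bias are unknown. The scenario of about 10% false positives for a 1-day shift (8.5% to 17.6% over the correlations tried) assumes 18 per arm, a 4.5-day SD and no true effect; it shows sensitivity and does not estimate this trial's error rate.

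A reader might go further and infer that the trial's type I error is in fact 10% to 26%, that all participants know their arm throughout the baseline, or that adjustment is useless. The documents support none of these: they give no shift, no time of disclosure and no correlation, and adjustment removes part of the bias.

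**What to change.** In 1.2, 1.3, 4.1 and 6.3, place randomisation after the fourth weekly baseline survey and the baseline PSQI and TBI-QOL are submitted and eligibility is reconfirmed, and before Visit 2 is booked. If the randomisation step itself cannot move, withhold the assignment from staff and participant until that same point and say so in 6.3.

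Count people who leave before that point as pre-randomisation screen failures. The replacement sentence in 7.2 and the open-ended screen-failure definition in 5.4 then have little left to cover and should be aligned with the new order. Account in the report for everyone randomised, including anyone replaced.

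Cost: an amendment and a later release of the assignment, with no new visit, data item or participant, and no change to the power calculation. Sessions are booked later, within the existing +14-day window. The amendment history (10.4) shows the protocol at version 11 with enrolment under way, so a change now could leave two groups with different baseline conditions. Participants already randomised under the present schedule should be identified, with the date on which each learned the arm where it is known, and examined in a sensitivity analysis. If practice has in fact been to randomise after the diary, correcting the grid, the Schema and 4.1 to say so is enough.
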